### Protocol version history:

IND Version #	Version Date	Major Changes
1.0	14 January 2020	Initial document
2.0	23 July 2020	Changed time of second biopsy from week 12 to week 4
3.0	30 September 2020	Added RNA Tape Stripping
4.0	28 October 2020	Modified biopsy protocol
5.0	29 January 2021	Removed RNA Tape Stripping and added virtual visits

**List of Abbreviations****LIST OF ABBREVIATIONS**

AE	Adverse Event/Adverse Experience
BSA	Body Surface Area
CFR	Code of Federal Regulations
CRF	Case Report Form
DEGs	Differentially Expressed Genes
DSMB	Data and Safety Monitoring Board
FDA	Food and Drug Administration
GCP	Good Clinical Practice
GVHD	Graft Versus Host Disease
HIPAA	Health Insurance Portability and Accountability Act
IB	Investigator's Brochure
IL-1	Interleukin-1
IND	Investigational New Drug Application
IFN $\alpha$	Interferon Alpha
IFN $\gamma$	Interferon Gamma
IRB	Institutional Review Board
JAK	Janus Kinase
NL	Necrobiosis Lipoidica
NRS	Numerical Rating Scale
PGA	Physician Global Assessment
PHI	Protected Health Information
PI	Principal Investigator
SAE	Serious Adverse Event/Serious Adverse Experience
SOP	Standard Operating Procedure
DM	Diabetes Mellitus
SCC	Squamous Cell Carcinoma

**Study Summary**

Title	Ruxolitinib Cream in the Treatment of Necrobiosis Lipoidica
Running Title	Ruxolitinib Cream in NL
Protocol Number	
Phase	Phase II
Methodology	Open-Label, Single Arm
Overall Study Duration	17 to 20 weeks
Subject Participation Duration	16 weeks
Single or Multi-Site	Single Site
Objectives	To evaluate the safety and efficacy of ruxolitinib cream in NL as assessed by the change in NL score (0-12) of the index treatment lesions, Pruritus NRS, Skindex-16, Physician Global Assessment (PGA), and BSA. To predict responses through the identification of unique biomarkers of NL at week 0 and utilizing RNA sequencing on responsive and non-responsive tissue at week 12.
Number of Subjects	12
Diagnosis and Main Inclusion Criteria	Non-pregnant adults with cutaneous NL up to 10% of the body surface area (BSA).
Study Product, Dose, Route, Regimen	Ruxolitinib cream 1.5%, topical application, twice daily on lesions of NL.
Duration of Administration	Drug will be administered from Day 0 through Week 12.
Reference therapy	Ruxolitinib cream has been studied in the treatment of plaque psoriasis and is under investigation in treating atopic dermatitis and vitiligo.
Statistical Methodology	The statistical analysis will provide descriptive summary statistics for categorical and continuous outcomes. Categorical variables will be described by their count and proportion of occurrence while continuous, normally distributed variables will be described by their mean and standard deviation; and continuous, non-normally distributed variables will be described by their median and range.

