#### 1.4 Clinical Data to Date

Plasma concentrations of ruxolitinib cream were determined following topical application of ruxolitinib cream in plaque psoriasis, AA, AD, and vitiligo, mostly using sparse sampling. The exposures of ruxolitinib were generally strength-dependent with moderate intersubject variability.

In Study INCB 18424-201 in plaque psoriasis, the observed systemic bioavailability of ruxolitinib was independent of formulation strength.

In Study INCB 18424-202 in plaque psoriasis, an intensive sampling scheme was used on the last day of treatment to better characterize the PK following topical application. The systemic PK following topical application was characterized by apparent first-order release, modest peak-to-trough excursion (ratio ~2), estimated relative bioavailability of 3% to 5%, and an  $t_{1/2}$  of approximately 3 days. Systemic bioavailability of ruxolitinib cream was shown to be independent of the strength of the cream formulation and %BSA. The PD results from skin biopsies, including markers for Th1, Th17 pathway activation, reduced levels of inducible nitric oxide synthase, and KRT16 transcript levels, suggest that ruxolitinib cream was pharmacologically active at a local but

not systemic level when administered to participants with active psoriasis for 28 days as either a QD or BID regimen and suggest that key pathologic pathways in the psoriatic lesion are favorably impacted by treatment with ruxolitinib cream.

In Study INCB 18424-204 in AA, ruxolitinib trough concentrations increased as percentage scalp involvement increased.

In Study INCB 18424-206 in AD, trough plasma concentrations increased as the strength of ruxolitinib cream and frequency of applications increased. Participants whose plasma concentrations exceeded 125 nM (equivalent to half of the IC50 value based on the effect of ruxolitinib on IL-6) tended to have more extensive skin involvement and highly inflamed AD lesions. However, no correlation was observed between higher ruxolitinib blood levels in these participants and their response to treatment.

In Study INCB 18424-102 in AD patients, steady-state plasma concentrations (based on geometric mean) following BID administration of 1.5% ruxolitinib cream in adolescent participants were similar to that in adult participants.

In Study INCB 18424-211 in vitiligo, plasma concentrations of ruxolitinib increased as the strength and frequency of application of the cream were increased.

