**Exploratory Objectives:**

To predict responses and examine the pharmacodynamics of treatment through the identification of unique biomarkers and transcriptomic changes of NL at week 0 and utilizing RNA sequencing on responsive and non-responsive tissue at week 4 To correlate these biomarkers with measures of global response: NL Lesion Score, PGA, and BSA.

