#### Exploratory Outcome Measures:

To predict responses and examine the pharmacodynamics of treatment through the identification of unique biomarkers and transcriptomic changes of NL at week 0 and utilizing RNA sequencing on responsive and non-responsive tissue at week 12 if data allows to correlate these biomarkers with measures of global response: NL Lesion Score, PGA, and BSA.

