# 7 Statistical Plan

## 7.1 Sample Size Determination

Data analysis: Due to the costs associated with a study, we propose a single armed study of 12 subjects with corollary science including RNA sequencing. This will reduce costs and provide

biomarkers predictive of response. Effect sizes will be estimated for the appropriate statistical tests that will be used for group comparisons in future studies. This will enable more accurate power and sample size estimates moving forward.

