### Bioinformatic Analysis:

RNA-seq analysis: We will use our recently developed LinNorm program

to process RNA-seq data and detect differentially expressed genes (DEGs) by comparing the RNA-seq profiles. We will first find DEG between responsive and non-responsive samples from the same individual by using paired or unpaired Wilcoxon rank-sum test (depending on how the samples are collected). We will then rank each gene in the DEGs based on the occurrence frequencies in all 12 subjects to find common DEGs for responsiveness (use permutation test to determine the p value). By comparing the normal tissue with the pathogenic tissue (responsive + non-responsive) using the above approach, we will detect a common DEGs for NL pathogenesis. Hierarchical clustering and Principal Component Analysis (PCA) will be applied to samples for their hierarchical relationship and clustering properties. Ideally normal, responsive and non-responsive tissues should form three distinct groups. The PCA analysis will provide us a set of gene signatures that can distinguish these three types of tissues. The common DEGs for responsiveness and pathogenesis, as well as gene signature from PCA will be used for our pathogenesis or survival

prediction. Additionally, we will perform de-convolutional analysis, to compare the immune profiles of responsive and non-responsive tissue and to correlate immune profiles. Predictive biomarkers will be correlated with lesional and global responses.

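### Response is to be predicted from week 0 biomarkers, but the only specified responsiveness analysis uses treated tissue, and no comparison of Day 0 lesional expression by later response is specified

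*Combined protocol and SAP*

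**What the plan says.** **Aim.** The Study Summary sets out to "predict responses through the identification of unique biomarkers of NL at week 0 and utilizing RNA sequencing on responsive and non-responsive tissue" and dates that tissue to week 12. The Exploratory Objectives in section 2 state the same aim but with "utilizing RNA sequencing on responsive and non-responsive tissue at week 4". The Exploratory Outcome Measures in 3.1 have "utilizing RNA sequencing on responsive and non-responsive tissue at week 12", with the proviso that the data allow it. Section 7.1 offers "biomarkers predictive of response" as one return on the single-arm design.

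**Tissue.** Under 3.1 every NL lesion is treated from the start. Each subject gives one lesional and one non-lesional biopsy at week 0, then one biopsy of a treated lesion at week 4. Up to 36 samples are sequenced. Table-2 shows biopsies at Day 0 and Week 4 only.

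**Analysis.** In 7.2, Bioinformatic Analysis, the responsiveness step reads: "We will first find DEG between responsive and non-responsive samples from the same individual". The genes are then ranked by how often they occur across the 12 subjects. Normal tissue is compared with the responsive and non-responsive tissue combined, and a PCA is expected to separate these three tissue types. The resulting genes and PCA signature go forward to prediction, and the section closes with: "Predictive biomarkers will be correlated with lesional and global responses".

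**The concern.** A biomarker that predicts response in the sense of the stated aim has to be measured before treatment. Expression in treated tissue may already reflect what the drug has done. A gene that differs there between responders and non-responders may have differed at baseline, or may differ because one group's lesions are improving.

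If 7.2 is followed as written, genes from treated tissue would be reported as predictive of response although they might be no use for choosing patients before treatment. Genuine baseline predictors that the drug brings back to normal would be missed. The samples that could answer the question are already being taken, so the loss is avoidable.

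**Working it through.** **1. Samples.** 12 subjects × (1 Day 0 lesional + 1 Day 0 non-lesional + 1 Week 4 treated) = 36, which matches the figure in 3.1. The tissue therefore divides into 12 untreated lesional, 12 untreated non-lesional and 12 treated lesional samples.

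**2. Which tissue carries the response label.** Section 7.2 does not date the responsive and non-responsive samples. The Exploratory Objectives say week 4; the Study Summary and the Exploratory Outcome Measures say week 12. Treatment runs from Day 0 to Week 12 (5.2), so on either date the tissue has been treated. Only the week 4 biopsy exists in the schedule.

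**3. The within-individual contrast.** One treated biopsy per subject is either responsive or non-responsive, never both. Even if the Day 0 lesional sample stood in for the other class, the comparison is 1 vs 1, and the smallest two-sided exact rank-sum p is 2/C(2,1) = 1. The step can only be run between subjects.

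**4. A gene that is a consequence of response.** All effect sizes here are assumptions; the documents give none. Response y ~ N(0,1); Day 0 expression g0 ~ N(0,1), independent of y; treated expression g4 = g0 − b·y + e, with e of SD 0.5. There are 12 subjects, a median split on y, an exact Mann-Whitney test of 6 vs 6 at p < 0.05, and 4,000 trials for b = 1 to 2.

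| b | flagged in treated tissue | flagged at Day 0 |
|---|---|---|
| 0.25 | about 7% | about 4% |
| 0.5 | about 14% | about 4% |
| 1 | 38% | about 4% |
| 1.5 | 60% | about 4% |
| 2 | 76% | about 4% |

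For b = 1, 1.5 and 2 the AUC in treated tissue is 0.79, 0.86 and 0.90, against about 0.50 at Day 0. The Day 0 rate is the test's own false-positive rate. Repeat runs agree to within about 2 percentage points.

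A second model gives the same pattern. Here responders shift by 1, 2 or 3 SD on drug, the Day 0 to Week 4 correlation is 0.5, and 4 or 6 of 12 respond. The gene is flagged at Week 4 in 28–30%, 81–83% and 98–99% of trials, against 4–5% at Day 0.

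**5. A true predictor that the drug normalises.** With Day 0 expression rising 1, 1.5 or 2 SD per SD of response and no association left at Week 4, it is found at Day 0 in 45%, 68% and 82% of trials, but at Week 4 in only about 4%.

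**6. A true predictor that persists on drug.** With a slope of 1 to 2 SD it is flagged in treated tissue in about 40% to 77% of trials. That is practically the rate in step 4, as it must be: b·y + N(0,1) + e has the same distribution as g0 − b·y + e apart from the sign of b. Treated tissue alone cannot tell the two kinds of gene apart.

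**7. What Day 0 tissue can support.** For a responder vs non-responder rank-sum test the smallest two-sided exact p is 2/C(12,r):

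- 6 vs 6: 2/924 = 0.0022
- 4 vs 8: 2/495 = 0.0040
- 2 vs 10: 2/66 = 0.0303
- 1 vs 11: 2/12 = 0.167

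Bonferroni over 594 genes (the size of the immune panel in 1.1, used as a low count) needs 0.05/594 = 0.000084. Over an assumed 20,000 genes it needs 0.0000025. No single gene can pass at any split.

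A correlation with the continuous change score has no such hard floor but is imprecise. For an assumed r of 0.6, Fisher's z is 0.693 ± 1.96/√9 = 0.693 ± 0.653, an approximate 95% interval for r of 0.04 to 0.87.

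**The case against.** **Week 0 biomarkers are promised a link to response.** Sections 2 and 3.1 name week 0 biomarkers and then a correlation with NL score, PGA and BSA, and 7.2 repeats a correlation. This stands. A reader might infer that the Day 0 biopsies are shut out of every response analysis, and the documents do not support that. What is missing is a tissue, a time point and a method.

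**The response label might be applied to Day 0 tissue.** Section 7.2 leaves the tissue undated and compares it with normal skin, which is taken only at Day 0. This reading is possible, but all three dated statements of the aim place responsive and non-responsive tissue at week 4 or week 12.

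**The simulation assumes what it shows.** Its effect sizes have no source in the plan, small effects give rates of only 7% to 14%, and it tests between subjects where 7.2 plans a within-individual contrast. All true. It shows what can happen to one kind of gene, not the make-up of a list. A reader might infer that the list will hold consequences instead of predictors; step 6 shows why that goes too far.

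**The supporting pharmacology is from psoriasis.** Section 1.4 reports after 28 days that "key pathologic pathways in the psoriatic lesion are favorably impacted by treatment with ruxolitinib cream". This makes a drug effect on Week 4 tissue plausible. It does not show one in NL, or one that differs by response.

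**Week 4 expression may be a legitimate early predictor.** It precedes the Week 12 endpoint by eight weeks, so it can be studied as an early on-treatment marker. It cannot select patients before treatment.

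**The aim is exploratory, in a study meant for estimation.** This limits the weight of the point. It does not justify the label, since 7.1 gives predictive biomarkers as a reason for the design.

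**Conclusion.** The point holds as a mismatch between aim and specified analysis. The only responsiveness step in the plan rests on tissue that its objectives and outcome measures date after treatment began, its genes feed prediction, and no comparison of Day 0 lesional expression by later response is specified. As written, the within-individual step cannot be run either.

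The size depends on assumed effects. A gene with no baseline relation to response is flagged in treated tissue in about 7% to 14% of trials for b = 0.25 to 0.5 and 38% to 76% for b = 1 to 2, against about 4% at Day 0. A normalised true predictor falls to about 4% at Week 4. The dating of the tissue and the count of one treated biopsy per subject need no such assumptions.

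The primary endpoint is untouched. The change should be made because the exploratory aim could otherwise be answered from the wrong tissue.

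**What to change.** Amend 7.2 and align the Study Summary, the Exploratory Objectives in section 2 and the Exploratory Outcome Measures in 3.1:

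- **Baseline prediction.** The predictor is Day 0 lesional expression, optionally lesional minus non-lesional, and Day 0 blood if it is sequenced. The outcome is the Week 12 change in NL score, analysed across subjects. A rank correlation would need no responder cut-off; if responders are compared, state the measure, cut-off and visit.
- **On-treatment markers.** Week 4 contrasts, and Week 4 minus Day 0 contrasts, are labelled pharmacodynamic or early on-treatment markers, not baseline predictors. Replace the within-individual responsive vs non-responsive step with a between-subject one.
- **Dates.** Reconcile the week 4 and week 12 statements with the biopsy actually scheduled at Week 4.
- **Reporting.** Give effect sizes with intervals and state that 12 subjects allow estimation only.

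The cost is wording. The Day 0 lesional biopsies are already among the 36 samples, so no visit, biopsy or tissue sequencing is added. The downside is that fewer genes can be called predictive, and those will carry wide intervals.

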## 1 Introduction

This document is a protocol for a human research study. This study will be carried out in accordance with the applicable United States government regulations and Mayo Clinic research policies and procedures.

### 1.1 Background

Necrobiosis lipoidica (NL) is a chronic, disfiguring, relapsing-remitting inflammatory disease primarily involving the lower extremities. NL disproportionately afflicts younger patients and is classically associated with diabetes mellitus (DM). Clinically, NL presents with atrophic yellow telangiectatic plaques that ulcerate in 30% of patients.

Although multiple therapies have been used to treat NL lesions, experience is largely anecdotal and there is paucity of data to guide effective treatment. Topical, intralesional, and systemic corticosteroids have been effective in a small number of non-DM patients; however, corticosteroids are high-risk treatment option in diabetic patients because they increase blood glucose levels and promote insulin resistance. Various non-steroidal immunosuppressants have been used, including methotrexate, tumor necrosis factor alpha inhibitors, mycophenolate mofetil, and fumaric acid esters, all with mixed success. Better treatment options with acceptable risk/benefit profile are clearly needed.

To characterize NL at the molecular level, we performed RNA sequencing to identify underlying immune mechanisms and possible therapeutic targets. We sequenced 18 representative NL tissues and 5 normal skin tissues, and identified deregulated genes enriched for immune system functions. Independent validation was performed using a Nanostring expression panel (594 immune-specific genes), demonstrating high concordance in the set of genes identified as differentially expressed by both platforms. Upregulated immunologic processes/pathways included those involved in T-helper cell induction, dendritic cell maturation, macrophage stimulation, and autoimmunity, indicating diverse immunological pathways are active in NL.

Importantly, we focused on identifying targetable “drivers” of downstream RNA expression changes. We prioritized such driver genes using by querying multiple drug databases in order to identify clinically targetable drivers. Using stringent criteria, we identified JAK1/2 and IFN $\gamma$  as key, activated drivers, and ruxolitinib as one of the most highly rated potential therapeutics in this search.

Interestingly, a recent report of an individual with polycythemia vera and NL reported near total resolution of his ulcerated NL upon treatment with oral ruxolitinib. Based upon our discovery of JAK-induced immune upregulation, we propose an open label, single arm study of topical ruxolitinib cream for NL patients to determine the effect of JAK inhibition on NL lesions. The primary objective will be the assessment of the impact of topical ruxolitinib cream on NL in a pilot setting, with the secondary objective being safety of treatment in NL patients. In order to further understand the responses, investigate the molecular effect of JAK inhibition, and explore

potential biomarkers, we propose to RNA sequence tissue and peripheral blood mononuclear cells pre- and post-treatment.

## 1.2 Investigational Agent

Ruxolitinib is an inhibitor of the JAK family of protein tyrosine kinases. Mitogenic and inflammatory cytokines are strongly implicated in the pathogenesis of psoriasis, alopecia areata, atopic dermatitis, and lichenoid tissue reactions of the skin including NL. Ruxolitinib cream also potently inhibited the phosphorylation of STAT proteins and the production of pro-inflammatory factors induced by cytokines such as IL-23 and IFN $\gamma$ . (Investigator's Brochure)

Ruxolitinib cream 1.5%, topical application will be used twice daily on lesions of NL.

## 1.3 Preclinical Data

Ruxolitinib potently (IC50 < 5 nM) inhibits JAK1 and JAK2, yet it does not significantly inhibit (< 30% inhibition) a broad panel of 26 kinases when tested at 200 nM (approximately 100 times the average IC50 value for JAK enzyme inhibition). Moreover, in cell-based assays relevant to the pathogenesis of inflammatory skin diseases, such as IL-2-stimulated phosphorylation of STATs and IL-2-induced proliferation of T cells, ruxolitinib demonstrates excellent potency (IC50 values of 10 to 40 nM). This effect was not due to general cytotoxicity because ruxolitinib (up to 10  $\mu$ M) had no effect on the survival of resting T cells (without IL-2 stimulation). Ruxolitinib also potently inhibited the phosphorylation of STAT proteins and the production of proinflammatory factors induced by cytokines such as IL-23 and IFN- $\gamma$ . Topical application of ruxolitinib demonstrated excellent efficacy in an in vivo model of immune-based skin inflammation, the DTH model in mice, including reduced ear swelling, reduced immune cell infiltrates, and normalization of tissue histology. Further, ruxolitinib was also efficacious in the inflammatory phase of the dorsal DTH model when applied in a clinically relevant cream formulation. In summary, pharmacological data obtained with in vitro and in vivo model systems support the use of topically applied ruxolitinib cream in the treatment of psoriasis, AD, vitiligo, and other inflammatory diseases of the skin. For all preclinical data below, please refer to the IB for more details.

The absorption, PK, distribution, and metabolism of ruxolitinib were characterized in CD-1® mice, rats, cynomolgus monkeys, beagle dogs, and Gottingen minipigs. The metabolism of ruxolitinib was characterized in vitro in the rat, dog, and human and in vivo in the CD-1 mouse, rat, dog, minipig, and human. The toxicologic and toxicokinetic profiles of ruxolitinib were characterized in rats, dogs, rabbits and the Gottingen minipig. Additional studies include the mass balance excretion of C-ruxolitinib in rats, dogs, and humans after oral dosing, the tissue distribution in rats after an oral dose, and the skin distribution in Gottingen minipigs after daily topical application.

Based on human data, the relative bioavailability of ruxolitinib cream was markedly (~90%) lower than that following oral administration. The primary clearance pathway is via metabolism. *In vitro* metabolism studies show that CYP3A4 is the predominant CYP isozyme responsible for the metabolism of ruxolitinib.

Ruxolitinib cream (up to 1.5%) was well-tolerated when applied daily for up to 9 months in the Gottingen minipig. Observed decreases in lymphocytes were considered nonadverse in the absence of any other findings suggestive of systemic toxicity. Ruxolitinib did not induce contact sensitization, and dermal and ocular irritation was minimal to negligible. Ruxolitinib does not have acute phototoxicity or photoallergic potential. There was no evidence of systemic toxicity following repeated ocular administration to rabbits or dogs.

Ruxolitinib administered as a single oral dose produced adverse effects on respiratory function in rats and blood pressure in dogs at exposures that were several-fold higher than in patients administered ruxolitinib cream.

Administration of oral ruxolitinib to juvenile rats beginning at Days 7, 14, or 21 postpartum (approximately equivalent to a human newborn, 1-year-old, or 2-year old, respectively) resulted in effects on growth and bone. In animals administered ruxolitinib beginning on Day 21 postpartum, the NOAEL was considered to be 15 mg/kg per day. There was no indication of a generalized or persistent effect on bone growth. Systemic exposure at this dose was several-fold higher than that observed in patients administered ruxolitinib cream.

Oral administration of ruxolitinib to pregnant rats and rabbits resulted in maternal toxicity and minimal embryo-fetal toxicity only at the highest doses evaluated. Ruxolitinib was not teratogenic in either species. The NOAEL for both rats and rabbits was 30 mg/kg per day. In an evaluation of fertility and early embryonic development, no effects were noted on reproductive performance or fertility in male or female rats. Increases in postimplantation loss were noted at the higher doses. In a pre- and postnatal development study in rats, there were no adverse effects on embryo-fetal or postnatal survival, growth, and developmental parameters.

Ruxolitinib was not mutagenic or clastogenic, nor did it demonstrate potential for carcinogenicity in a 6-month study in Tg.rasH2 mice or in 2-year studies in mice or rats.

